4.2 Primary and secondary outcomes

The primary outcome on which our study is powered is 7-day point prevalence at 6 month follow-up, which, unlike continuous abstinence, allows for delayed quitting. Unlike traditional cessation trials, there is no uniform quit date for all participants in the current trial, and thus anchoring abstinence to a designated quit attempt is unrealistic. However, we will track a number of secondary outcomes, including 30-day point prevalence abstinence, and incidence, frequency, latency, and duration of quit attempts (both self-defined and those lasting >24hrs), as well as smoking reduction (% reaching 50% reduction between baseline and end-of-study), provider acceptability and cost-effectiveness.

4.3 Inclusion/exclusion criteria

General Inclusion / exclusion criteria are as follows:

- a) age ≥ 18
- b) daily (25+ days within past 30) cigarette smoker of ≥ 5 cigs/day
- c) English speaking
- d) recruited through primary care sites aligned with study
- e) no FDA contraindications for use of NRT:
 - a. not pregnant, breastfeeding, or planning to become pregnant
 - b. no recent (past 3 months) cardiovascular trauma: MI, stroke

4.4 Sample Size

The sample size is 1300 participants. Section C.10 of the grant text provides a detailed rationale for why this sample size was chosen.

In anticipation of potential budget cuts, we will reduce the number of clinics that enroll, and we have in fact identified 8 clinics that could be removed, with offset increases in per-clinic enrollment within remaining 20 clinics. Our minimum number of clinics to participate is 20. Also, as the study progresses, we do expect some changes in clinic involvement, for any number of reasons (e.g., change in clinic staff, change in structure/volume, etc). The table above merely represents the 28 clinics from which we anticipate we will select our 20 final clinics. Appropriate amendments will be obtained in advance of all such changes. Changes in clinic involvement will be noted in all progress reports sent to NIDA. The CCI network currently has 120 sites in South Carolina alone, of which 70 meet our inclusion criteria, and these numbers are increasing regularly, as CCI grows. If any one site is not able/willing to be included, we have ample additional sites to include.

4.6 Projected Timetable

The timetable is as follows:

	Year 1 (months)	Year 2 (months)	Year 3 (months)	Year 4 (months)	Year 5 (months)
Refine all procedures	1-6				
Procure supplies	1-6				
Refine recruitment methods	1-6				
Hire and train Central Personnel	5-8				
Hire & Train Additional Personnel*		13	25	37	
Pre-trial Focus groups (n=4)	7-8				
Train Clinic Personnel		Rolling, as new sites come on line			
Study Enrollment					
Cumulative Clinics to Begin Enrollment**	(2)	(7)	(13)	(17)	(20)
Cumulative N to start*** ^a	(116)	(406)	(754)	(986)	(1300)
First Participant Starts	10				
First Participant Completes		16			
Last Participant Starts					50
Last Participant Completes					56
Data Analysis					56-60
Manuscript Preparation					56-60

* Additional study personnel beyond year one per budget justification; All numbers reflect months within total study duration (**with the exception of cumulative clinics to begin recruitment, and cumulative N); ^a assumes average of 58 participants recruited per clinic

4.7 Target Population

Women will be included in this protocol. Currently, women are about 50% of smokers (slightly less among African American women) and thus it is estimated that 50% of the study sample will be women. If there are discrepancies in terms of gender, efforts will be made to improve recruitment of women into the study through oversampling via online recruitment.

Minorities are also included in this study, and we have increased our estimates of minority enrollment to address reviewer concern from the initial grant submission. All participating sites in the CCI network (network of primary care providers) are based in South Carolina, where approximately 28% of the population is African American (<http://quickfacts.census.gov/qfd/states/45000.html>). We will aim for 28% enrollment of African Americans (all other minorities collectively comprise <5% of South Carolina population, reflected within target enrollment). We will monitor closely our minority recruitment goals on an ongoing basis and initiate oversampling of African Americans if recruitment rate of minorities drops below 25%.

4.8 Data Acquisition and Transmission

The study will be managed from the Division of Clinical Neuroscience within the Department of Psychiatry and Behavioral Sciences at the Medical University of South Carolina (MUSC), but physically based within the Cancer Control Program of the Hollings Cancer Center, where the PI is based. Recruitment will be coordinated through a consortium of primary care providers (CCI). Recruitment will be conducted at separate participating clinics, and intervention will be delivered locally at each clinic as well. All recruited participants will locally (within each clinic) sign a consent form and complete a baseline questionnaire. The consent form will be returned in a pre-addressed, pre-stamped envelope that we provide, and the baseline questionnaires will be completed in REDCap and securely transmitted to MUSC study staff electronically. Nothing beyond the baseline visit is conducted at the clinics; all follow-up data collection and management will be centrally managed at our research lab at MUSC.

4.9 Data Analysis Plan

All analyses are based on an intent-to-treat approach, and are nearly identical to analyses from our current and prior studies. Exploratory analysis will be performed on all variables to determine if transformations are needed. Any significant baseline differences between groups will be included in regression analyses described below. All analyses below will be run separately for full intent-to-treat sample (immediately below), per protocol, and, within the NRT group, using those participants who used single vs. combined NRT products.

Examination of Potential Site Differences Outcomes and patient characteristics will be estimated across clinics using summary statistics and confidence intervals. This will be considered an exploratory analysis due to the relatively large number of clinics and, hence, the large number of multiple comparisons that could arise. Grouped logistic regression modeling may be used to describe associations between clinic characteristics and binary clinical outcomes (e.g., quit rate).

Missing Data & Dropout The most conservative approach for handling missing data is to substitute them with baseline values, assuming outcomes have all returned to baseline, with no quit attempts made or abstinence achieved. If this assumption is incorrect, it biases the results towards the null by reducing between group differences. Since we expect few missing data, we will use this approach. If missing data >10%, we will calculate results using this conservative method but also using methods in which missing data are imputed as described in the SRNT guidelines. We will also assess whether dropout is differential by study group. In our current and recent studies of cessation induction, this has not been the case. Abstinence will be reported both with and without (missing samples) cotinine verification.

Hypotheses 1a, 2, & 3 These hypotheses predict that provision of NRT samples will lead to higher abstinence rates (Hyp. 1a), incidence of quit attempts (Hyp. 2), and uptake of additional treatment (Hyp. 3). Logistic regressions will be performed for each outcome with treatment group (standard care vs. NRT sampling)

as the covariate, estimated using generalized estimating equations (GEE) to account for clustering within clinic. Rates for each outcome will be estimated along with its 95% confidence interval. The coefficient on group will be evaluated using a Wald test to determine if the abstinence rates in the two arms are statistically significantly different at the one-sided 0.025 level. Additional regression modeling will be performed where covariates such as age, gender, and race are accounted for. We will also consider interactions between NRT and categorical covariates to determine if there are certain subgroups in which NRT sampling is more or less effective. Though we expect few individuals to make more than one quit attempt over the span of 6 months, and thus examine incidence of quit attempts (Hypothesis 2), we will examine the distribution of quit attempts, and if appropriate, examine number of quit attempts via Poisson regression modeling. In addition to binary outcomes of treatment uptake (Hyp. 3), we will test for continuous outcomes (e.g., treatment intensity, duration) via GEE regressions.

Hypotheses 1b Hypothesis 1b predicts that provision of NRT samples will result in longer period of abstinence (longest # days non-smoking) across the entire study duration, and will be evaluated using regression modeling via GEE accounting for clustering by clinic.

Secondary Analyses

Provider Acceptability We will provide separate, descriptive data on provider acceptance and satisfaction with treatment delivery. We do not plan any formal between group comparisons because of very limited sample size (14 clinics in each site). This study is not powered on provider-level outcomes of our intervention, but such data will be useful as we consider expanding our intervention into different venues.

Cost Effectiveness We will track intervention delivery costs (i.e., personnel, materials, NRT itself) per treatment group, though anticipate the only difference to be the cost of NRT. We will analyze and compare costs for intervention and control patients, for quit attempters vs. non-quit attempters, and for quitters vs. non-quitters. We will do this both across and within groups, and our model will adjust for patient characteristics, including demographics and smoking history. Led by our dissemination expert ([name]), we will examine differences in direct medical costs (from the EMR) of all medical care post study enrollment for a sample of all study participants, of all participants who quit smoking during the trial, and for all intervention participants. We expect to show that NRT sampling as a strategy is, at least in the short term cost neutral, if not cost saving.

Other We will also examine changes in cigarette smoking, motivation, confidence, attitudes/knowledge of NRT over time, as a function of treatment group. These continuous variables (absolute, and change since baseline) will be examined as per Hypothesis 1b above.

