Our **Primary Specific Aim** is to examine cessation outcomes of a large-scale (N=1300; 20 participating clinics) randomized clinical trial of 1) Standard Care, based on established guidelines (Ask, Advise, Refer [quitline referral]) vs. 2) Standard Care + NRT Sampling. Participants will be drawn from a network of primary care settings that has established infrastructure in which to embed clinical research. Randomization will be at the clinic level, but individual participants represent the unit of analysis. Identified smokers who meet eligibility criteria will be consented into a trial. Interventions will be delivered within the primary clinic directly by providers who are trained and monitored on study procedures. All participants will receive advice to quit and referral to state quitlines. Half of the sample will receive a small token bag that includes samples (i.e., 1-2 week starter kit) of both nicotine patch and lozenge. Follow-up assessment (through 6 months) will track both primary (abstinence, quit attempts, use of additional treatment) and secondary (motivation, confidence) outcomes. Our team has strong experience in such trials, including methods to efficiently recruit and effectively retain large numbers of smokers in clinical research. Our principle hypotheses are as follows:

Hypothesis 1a: As compared to Standard Care model of physician-delivered brief advice (Ask, Advise, Refer), provision of brief advice + NRT samples within primary care setting will result in a higher abstinence rates (7-day, point prevalence at 6 month follow-up).

Hypothesis 1b: Brief advice + NRT sampling will result in longer period of abstinence (longest # days non-smoking) across the entire study duration.

Hypothesis 2: NRT sampling will result in higher rates of quit attempts (any self-defined and any 24hr quit attempt).

Hypothesis 3: Brief advice + NRT sampling will result in higher subsequent uptake of evidence-based treatment (behavioral, pharmacological assistance).

NRT sampling represents a brief, concrete, easy to explain strategy that both healthcare providers and smokers readily accept. Thus, it is uniquely suited to the primary care setting, and could be a novel, behaviorally based intervention to promote quitting. If so, NRT sampling holds great significance on both a clinical and policy level.

Human Subjects Research**1. Risks to Human Subjects****1.1 Human Subjects Involvement and Characteristics**

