4.10 Quality Assurance Plan

Data will be collected centrally by our research staff rather than locally at each clinic. Computerized data collection methods (Redcap) optimize quality assurance. Redcap system does not accept outliers, illogical response patterns, etc. The PI will have weekly meetings with the research assistants to discuss qualitative comments received during data collection and any problems in data collection. The statistician will periodically examine the database to look for irregularities. Initial data analyses will examine distributions of variable scores, comparability of baseline characteristics, follow-up rates and use of extra-study cessation treatment across conditions in case analyses need to be adjusted for these.

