4.13 Trial stopping rules

There are three potential reasons to stop the trial prematurely: a) undermining of cessation, b) higher-than-anticipated quit rates, and c) significant rate of adverse events. Each is addressed below.

a) To protect against undermining of cessation, we will form a Data Safety and Monitoring Board (DSMB) and have them conduct an interim analysis after 50% of the sample has completed 6 month follow-up. We chose this number as this is the minimum necessary given our base rate is projected to be 15% and one has to see clear trend toward an even lower rate. To do this, the statistician will provide a copy of the dataset to the board. If this occurs, this board will independently decide on whether to stop the study.

b) We plan to examine the data halfway through enrollment to determine if observed differences in quit rates are so large that the trial should be stopped early. Using the method of O'Brien and Fleming (129) the significance level for this interim analysis is $\alpha = 0.005$. According to this same reference, conducting this analysis decreases our power for detecting our projected differences only from 0.80 to 0.79.

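### Section 4.9 adds any significant baseline difference to the regressions but defines the primary model with treatment group alone, so the model that decides Hypothesis 1a can depend on the data

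*Combined protocol and SAP*

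**What the plan says.** The opening paragraph of section 4.9 sets a rule for all the regressions that follow: "Any significant baseline differences between groups will be included in regression analyses described below". It names no candidate variables, no test and no threshold.

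Under Hypotheses 1a, 2 and 3, the same section describes logistic regressions with treatment group "as the covariate, estimated using generalized estimating equations (GEE) to account for clustering within clinic". The decision rule follows: "The coefficient on group will be evaluated using a Wald test", at the one-sided 0.025 level. Adjusted models come after that: "Additional regression modeling will be performed where covariates such as age, gender, and race are accounted for".

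Section 4.10 adds that initial analyses will look at "comparability of baseline characteristics, follow-up rates and use of extra-study cessation treatment across conditions in case analyses need to be adjusted for these". Hypothesis 3 in the Specific Aims makes treatment uptake an outcome in its own right: "Brief advice + NRT sampling will result in higher subsequent uptake of evidence-based treatment".

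Sections 4.13(b) and 4.17 plan an efficacy look at alpha 0.005 ("We plan to examine the data halfway through enrollment") and name no model. Section 4.1 states that clinics, not patients, are randomised.

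**The concern.** If any baseline variable is significant, the selection rule and the group-only model cannot both be followed in one analysis of Hypothesis 1a, and no passage ranks them. Two statisticians working from this plan could report different primary odds ratios and occasionally different verdicts, each with textual support.

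The rule is also a poor one. In a randomised trial an imbalance p-value picks variables for chance difference, not for prognostic value. With clinics randomised, a patient-level test that ignores clustering flags far more variables than a clinic-level test, and the plan does not say which applies. A rule re-run at the interim and at the end may pick different covariates each time.

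The sentence in section 4.10 is a separate exposure. Follow-up rates and outside treatment both arise after randomisation. Sampling is meant to raise treatment uptake, so adjusting abstinence for uptake would remove part of the effect under test.

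**Working it through.** **1. The plan's own figures.** A two-look O'Brien-Fleming boundary at overall two-sided 0.05 has a final critical value of 1.977 and an interim value of 1.977 × √2 = 2.796. The interim two-sided level is then 0.0052 (stated: 0.005), and a fixed-design power of 0.80 becomes 0.797 (stated: 0.79). These agree. N = 1300 cannot be reproduced, because section 4.4 refers to grant text that is not in the document. With 15% control abstinence (section 4.13(a)), 650 per arm, one-sided 0.025 and no clustering, 21% in the NRT arm gives power 0.805. I therefore took about 15% v 21% as the working effect.

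**2. How often the rule fires.** For K independent variables tested at an assumed two-sided 5%, the chance that at least one enters is 1 − 0.95^K: 23% (K = 5), 40% (K = 10), 64% (K = 20). If the test ignores clinics of 65 (1300/20), the design effect is 1 + 64ρ and the chance per variable is 2[1 − Φ(1.96/√DE)]:
- ρ = 0.01: DE = 1.64, 12.6% per variable, 1 − 0.874^10 = 74% for ten.
- ρ = 0.05: DE = 4.20, 33.9% per variable, 1 − 0.661^10 = 98% for ten.

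**3. Simulation.** From the documents: N = 1300, 20 clinics, 15% base rate. Everything else is assumed:
- 10 v 10 clinics of 65.
- Ten normal baseline variables, ICC 0.01 or 0.05. Four are prognostic, with log OR per SD of 0.40, 0.25, −0.25 and 0.10 (full strength) or half of these.
- Residual outcome ICC 0, 0.01 or 0.02. Conditional log OR 0 or 0.45 (21.2-21.6% abstinence in the NRT arm).
- Independence working correlation, clinic-robust SE scaled by G/(G−1), t on 18 df, one-sided 0.025.
- 4,000 trials in each of 24 cells.

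| | Clinic-level imbalance test | Test ignoring clinics |
|---|---|---|
| At least one variable enters | 39-42% | 73-99% |
| Verdicts differ, effect present | 0.9-3.0% | 1.7-9.5% |
| Verdicts differ, null | 0.1-0.7% | 0.3-2.1% |
| Different covariate set at half-sample interim and at end | 50-54% | 79-98% |

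When a variable enters, the odds ratio moves by a factor of 0.90-1.12 (5th-95th percentile) in the strongest scenario and 0.97-1.04 in the weakest.

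| Outcome ICC | Power, group only | Power, selection rule | Power, fixed list of five |
|---|---|---|---|
| 0 | 77.8-85.0% | 78.2-85.0% | 83.0-85.4% |
| 0.01 | 58.1-62.8% | 58.0-62.7% | 62.0-64.1% |
| 0.02 | 47.0-49.2% | 46.7-49.8% | 48.7-50.4% |

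The fixed list (the four prognostic variables plus one null) gains 0.5-5.2 points over group only at full prognostic strength and 0.1-2.1 at half. One-sided type I error is 2.2-3.5% (group only), 2.2-3.4% (rule) and 2.2-3.4% (fixed list). Monte Carlo SE is at most 0.8 points on power and about 0.5 on paired differences.

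**4. Second simulation.** This used five or ten equally prognostic variables (log OR 0.25 per SD, ICC 0.01 or 0.02), tests ignoring clinics, an uncorrected robust Wald test at 1.96, and 3,000 trials per scenario. Verdicts differed in 0.9-2.1% of null trials and in 5.9% with a log OR of 0.42. Type I error was 3.6-4.4% for group only and 3.5-4.1% for the rule. Taking whichever model is significant gave 4.1-5.3%, which is 0.3-0.9 points above group only. The excess over 2.5% in every model comes from the uncorrected Wald test with 20 clinics and is a separate matter.

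**5. Adjusting for outside treatment (section 4.10).** Assume treatment doubles abstinence, control uptake is 20%, the direct odds ratio is 1.30, and uptake and abstinence are unconfounded.
- Control: 0.20 × 25% + 0.80 × 12.5% = 15.0%.
- NRT arm at 35% uptake: 0.35 × 30.2% + 0.65 × 15.7% = 20.8%.
- Total OR = 1.485; adjusted OR = 1.30; share of the log OR lost = 1 − ln(1.30)/ln(1.485) = 34%.
- At 25% and 45% uptake the total ORs are 1.36 and 1.62, and the losses are 14% and 46%.

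**The case against.** The best counter-reading is that section 4.9 comes close to naming the decision model. The only stated test and alpha belong to the group-only coefficient, and adjusted models are labelled additional. On that reading the selection rule feeds only the additional models and one clarifying sentence is enough. Three things stand against relying on it. The sentence after the rule uses *below* to include the main intent-to-treat analysis. The additional models list age, gender and race, not whatever is imbalanced. For Hypothesis 1b the selection rule is the only covariate rule given.

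Other objections limit the size of the point, and they stand:
- Following the rule mechanically does not inflate type I error and leaves average power within about half a point of group only. The larger discordance figures need an imbalance test that ignores clinics, which the plan never states, and the top of the range also needs a covariate ICC of 0.05.
- A changed covariate set at the interim has no demonstrated cost. With boundaries of one-sided 0.0026 and 0.024 (outcome ICC 0.01, full prognostic strength, 1,000 trials per cell), overall error was 2.5-3.6% for group only and 2.3-3.5% for the rule re-run at each look. Power was 57.5-58.7% and 57.3-58.7%.
- Section 4.10 is a conditional quality-assurance sentence that names no model, so the 14-46% loss illustrates an analysis the plan permits but does not commit to.
- The fixed-list power gain is a best case, because the list was built from variables made prognostic. With five null variables the difference was −0.6 to +1.2 points, which is simulation noise.
- The 2.2-3.5% type I error levels rest on a small-sample correction that section 4.9 does not mention.

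**Conclusion.** The concern holds. The plan states a data-dependent selection rule that conflicts with its stated primary model, and nothing in it resolves the conflict. The numerical harm is modest: discordant verdicts in about 1-3% of trials with an effect under a clinic-level imbalance test, and up to 9.5% under one that ignores clinics. These figures assume ten candidate variables, a 5% threshold, and the ICCs and prognostic strengths listed above. The case for changing it is that the primary result should be determined by the plan, identically at both looks, and should not be open to adjustment for something the intervention is meant to change. It should be corrected, but it does not threaten the trial's validity.

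**What to change.** Delete the selection sentence from section 4.9 and name one primary logistic GEE model for Hypothesis 1a in advance. Preferred: treatment group plus a short fixed list of baseline variables already collected, for example cigarettes per day, motivation, age, gender and race. Report the group-only model as supportive, and give marginal abstinence rates by arm and their difference. The alternative closest to the present text is group-only as primary with the fixed-list model as a sensitivity analysis. Either resolves the conflict.

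State in sections 4.13(b) and 4.17 that the interim uses the same model as the final analysis. State that the primary model will not be adjusted for follow-up rates or outside treatment use, and keep the section 4.10 checks descriptive.

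The cost is wording only, with no new data. The preferred option has downsides. Its odds ratio is conditional, so marginal rates must accompany it. With 20 clinics the list must stay short. A rule for missing baseline values is needed. The power gain may be near zero if the variables are weakly prognostic.

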4.1 Summary of the Protocol

The design calls for a 2-group, randomized clinical trial of 1) standard care (Ask, Advise, Refer) vs. 2) standard care + NRT sampling. Randomization will be at the clinic level, but the unit of analysis is the individual smoker. Following consent, baseline assessment, and provider intervention (all done within clinic), follow-up assessment (coordinated centrally through our study team) will continue at +1, +3, and +6 months. The primary outcome will be 7-day point prevalence abstinence at 6-month follow-up, though we track a number of other outcomes as well. A recent trial of comparative effectiveness for single/combined pharmacotherapy (79) provided strong framework for our decisions. As a comparative effectiveness study, our guiding philosophy is to optimize ecological (i.e., external) validity, while at the same time maintaining basic standards of scientific rigor.

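### Counting missing participants as smokers does not always bias towards the null: it can favour NRT, and no planned analysis is tied to unequal loss between arms

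*Combined protocol and SAP*

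**What the plan says.** The Missing Data & Dropout paragraph of section 4.9 replaces missing outcomes with baseline values, so a participant who is lost counts as smoking and as having made no quit attempt. It calls this the most conservative choice and adds: "If this assumption is incorrect, it biases the results towards the null by reducing between group differences".

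One alternative is promised, under one condition: "If missing data >10%, we will calculate results using this conservative method but also using methods in which missing data are imputed". The methods are those of the SRNT guidelines, which are not part of the documents.

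Retention by arm is not overlooked:

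- Section 4.9: "We will also assess whether dropout is differential by study group", followed by "In our current and recent studies of cessation induction, this has not been the case".
- Section 4.10: initial analyses will look at "follow-up rates and use of extra-study cessation treatment across conditions in case analyses need to be adjusted for these".
- Section 4.8: "all follow-up data collection and management will be centrally managed at our research lab".

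Neither check names a size of difference, a method, or an analysis that would follow from the result.

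**The concern.** The towards-the-null sentence gives the primary analysis a safety property before any data are seen. If it were always true, a positive result would need no defence against loss to follow-up. But the rule removes true quitters from each arm in proportion to how many were lost and how many of those had quit. If standard care loses more quitters than NRT does, the rule creates or enlarges a difference in favour of NRT. Section 4.9 tests one-sided at 0.025, so this is the direction that inflates the error the test is meant to control.

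The trigger does not guard against it. A level of missing data is not an imbalance, and the plan does not say whether the 10% is pooled or per arm. The same substitution applies to quit attempts (Hypothesis 2).

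**Working it through.** The disputed statement is qualitative, so the plan has no figure to reproduce. The check is algebra followed by illustrations.

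**Inputs from the documents.** N = 1300 (4.4), half receiving samples (Specific Aims), so 650 per arm. 20 clinics (Specific Aims), so 1300/20 = 65 per clinic. Base abstinence 15% (4.13). One-sided 0.025 Wald test on the group coefficient of a logistic GEE (4.9).

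**Assumptions.** Loss by arm, abstinence among those lost, and the intraclass correlation (ICC) are not given. ICC is taken as 0 to 0.01, so the design effect DE is 1 to 1 + 64 × 0.01 = 1.64.

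**Bias.** With true rate p, share missing m and abstinence among the missing q, the observed rate is o = p − m·q. Hence

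observed difference (NRT − control) = (pT − pC) + (mC·qC − mT·qT).

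The second term is the bias. It is zero if q = 0 in both arms, positive if mC·qC > mT·qT, and negative if the inequality is reversed.

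**Error rate with no true effect.** SE = √(DE × [oC(1−oC) + oT(1−oT)]/650); error = P(Z > 1.96 − difference/SE). This is a normal approximation to the planned test.

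Worked case, control 10% v NRT 6% missing, p = q = 15%: oC = 0.15 − 0.10 × 0.15 = 0.1350; oT = 0.15 − 0.06 × 0.15 = 0.1410; difference +0.6 points. SE = 0.0191 (DE 1) or 0.0245 (DE 1.64), so difference/SE = 0.314 or 0.245, and the error is 0.050 or 0.043.

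| Missing, control v NRT | q, control / NRT | Observed, control v NRT | Bias (points) | One-sided error, DE 1.64 to DE 1 |
|---|---|---|---|---|
| 10% v 8% | 15% / 15% | 13.50% v 13.80% | +0.3 | 0.033–0.036 |
| 10% v 6% | 15% / 15% | 13.50% v 14.10% | +0.6 | 0.043–0.050 |
| 14% v 5% (9.5% pooled) | 15% / 15% | 12.90% v 14.25% | +1.35 | 0.080–0.106 |
| 9% v 9% | 15% / 5% | 13.65% v 14.55% | +0.9 | 0.055–0.068 |
| 10% v 8% | 7.5% / 7.5% | 14.25% v 14.40% | +0.15 | 0.029–0.030 |
| 10% v 6% | 7.5% / 7.5% | 14.25% v 14.55% | +0.3 | 0.033–0.036 |
| any | 0 / 0 | 15% v 15% | 0 | 0.025 |

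In the reversed case, 6% v 10% with q = 15%, the bias is −0.6 points and the error falls to 0.0115 (DE 1) or 0.0137 (DE 1.64).

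A simulation of the 14% v 5% case without clustering, using a Wald test on the log odds ratio, gave 0.104 against the approximation's 0.106. If the 10% trigger is read as pooled, that case calls for no imputation, because (14 + 5)/2 = 9.5%.

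**With a true effect.** Assume 15% v 21%, with those lost quitting like those kept in their own arm. The true difference is 6.0 points and the true odds ratio (0.21/0.79)/(0.15/0.85) = 1.506.

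- *Equal 10% loss:* 13.5% v 18.9%, 5.4 points, odds ratio 1.493. Both move towards the null, as the plan says.
- *Control 10% v NRT 8%:* 13.5% v 19.32%, 5.8 points, odds ratio 1.534. The risk difference shrinks, but the odds ratio, the scale of the planned test, moves away from the null.
- *Break-even, risk difference:* 0.15·mC = 0.21·mT, so mC/mT = 1.4.
- *Break-even, odds ratio, at 10% control loss:* oT/(1−oT) must equal 1.506 × 0.135/0.865 = 0.2351, so oT = 0.1903 and mT = 1 − 0.1903/0.21 = 9.36%. The ratio is 10/9.36, about 1.07.

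**The case against.** The strongest reply is that the plan already deals with this in outline. It expects few missing data, reports no differential dropout in the team's current and recent studies, centralises follow-up, checks dropout by arm and leaves room for adjustment. With similar loss in both arms and a real benefit, the towards-the-null statement is right. Every loss figure above is assumed. At 10% v 8% the error rises only to 0.033–0.036, or to 0.029–0.030 if those lost quit at half the rate. The larger figures need a marked imbalance or a threefold difference in q.

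All of that stands, and it limits the size of the point. It does not rescue the unconditional sentence or supply the missing link from the checks to an analysis. A significance test of dropout would not supply it reliably: at two-sided 5%, it would flag 10% v 6% with probability only 0.55 to 0.76 over the same design effects.

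Stronger readings that the documents do not support:

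- *That differential dropout was ignored, or will occur.* Sections 4.9 and 4.10 check for it, and nothing in the documents predicts it.
- *That unequal loss always favours NRT.* More loss in the NRT arm can do the opposite. Nor does equal loss guarantee the stated direction, as the 9% v 9% row shows.
- *That bias runs away from the null only once control loss exceeds 1.4 times NRT loss.* That holds for the risk difference, not for the log odds ratio that is to be tested.
- *That imputation could never be triggered while both arms stay at or below 10% at month 6.* The trigger names no visit or sample, and contacts run at 1, 3 and 6 months, so it could be read more widely.
- *That the imputation methods are inadequate.* They are set by reference ("methods in which missing data are imputed as described in the SRNT guidelines") to a source not supplied, so they cannot be judged.

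**Conclusion.** The concern holds as a modest but real fault. The stated direction of bias is wrong as a general statement. That rests on algebra alone: the bias is mC·qC − mT·qT, which can take either sign. The gap in the rule is also plain from the text, since the trigger concerns the amount of missing data and the checks by arm lead to no named analysis.

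The size depends on assumptions. With no true effect and those lost quitting like those kept, imbalances of 2 to 4 points near 10% loss give +0.3 to +0.6 points and one-sided error of 0.033 to 0.050. A 14% v 5% split, which passes a pooled trigger, gives +1.35 points and 0.080 to 0.106. These figures illustrate what the rule allows and do not forecast this trial. The change should be made because it is cheap and because a conservative label should not be granted in advance.

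**What to change.** Keep missing = smoking as the primary rule, and make three changes in section 4.9.

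1. Replace the towards-the-null sentence with: *The direction of bias depends on dropout and on abstinence among those lost in each arm; it can favour NRT if standard care loses more participants who had quit.*
2. Whatever the overall level of missing data, run a sensitivity analysis of the primary outcome that varies abstinence among those lost separately by arm, over a bounded range stated in advance that includes unequal values. Alongside it, run an imputation analysis using arm, clinic, baseline and the 1- and 3-month data. Because neither waits for a trigger, both also cover equal loss with unequal abstinence among those lost.
3. Describe the primary result as conservative only if that analysis supports it.

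The cost is one reworded sentence and a modest amount of extra analysis. Follow-up "will continue at +1, +3, and +6 months" already provides the interim data, so no extra participants or visits are needed.
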